6.2 Sample Size and Power Determination

Because we have several outcome measures, and because there is little known about how TMS will affect these outcome measures, we are conducting a single power analysis to determine sample size, based on a moderate effect size of ($f=0.5$). If we set power at 0.8 and use a corrected two-tailed alpha of 0.025 we would need 26 subjects per group to detect a main effect. Assuming a 15% unusable data rate and 3 pilot subjects, we will need 63 total subjects. However, this will be updated prior to enrollment based on the best available information at the time. To ensure that we are adequately powered across the study arms, and to account for additional dropout due to scheduling issues, we plan to recruit up to 75 participants.

7 Safety and Adverse Events

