This research is significant because upon completion, we expect to have direct evidence for a causal role of the right dIPFC in anxiety regulation, complete with evidence

CONFIDENTIAL

of target engagement through simultaneous TMS/fMRI, and a novel application to anxiety. This research will lay the groundwork for my long-term career objective, which is to develop an independent, NIH-funded research program employing psychophysiology, neuroimaging, and neuromodulation in healthy and anxious participants aimed at developing a circuit-level understanding of the neurobiological mechanisms underlying anxiety.

2 Study Objectives

Aim 1: Determine the effect of a 1-week course of TBS treatment (Continuous vs. Intermittent; right dlPFC target) on anxiety using the unpredictable shock-threat paradigm. Our hypothesis, consistent with our pilot data, is that strengthening circuits in the right dlPFC will facilitate anxiety regulation. Accordingly, we expect excitatory but not inhibitory TBS (compared to sham) to reduce induced anxiety.

Aim 2: Determine the effect of a 1-week course of TBS treatment (Continuous vs. Intermittent; right dlPFC target) on anxiety-related WM-deficits using the Sternberg WM paradigm during threat of shock. Our hypothesis is that the rTMS will strengthen right dlPFC circuits, which will rescue the anxiety-related WM deficits. Accordingly, we expect that 10 Hz rTMS (compared to sham) will improve accuracy on the Sternberg WM task during threat.

Aim 3: Demonstrate target engagement by measuring BOLD responses evoked by TMS pulses to the right dlPFC during threat of shock. Our hypothesis is that direct stimulation of the right dlPFC will reduce ongoing anxiety-related activity. Accordingly, we expect active but not sham TMS pulses to the right dlPFC to evoke BOLD deactivations in regions of the fear/anxiety network (i.e. amygdala, BNST, anterior insula).

3 Investigational Plan

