6.1 Primary Endpoints

Aim 1: Determine the effect of a 1-week course of TBS treatment (Continuous vs. Intermittent; right dlPFC target) on anxiety using the Neutral, Predictable, and Unpredictable (NPU) shock-threat paradigm.

Outcome measures. Fear potentiated startle (FPS) will be calculated by subtracting the blink magnitude during the predictable inter-trial interval (ITI) from the predictable cue. Anxiety potentiated startle (APS) will be calculated by subtracting the blink magnitude during the neutral ITI from the unpredictable ITI. Online anxiety ratings will be processed similarly.

Statistical Analysis. The main analysis will be a 3 [stimulation: pre-stimulation vs. post-active vs. post-sham] by 2 [protocol: cTBS vs. iTBS] repeated-measures ANOVA. In addition to the main factors considered, we may also co-vary out several individual difference measures (e.g. baseline anxiety via self-report questionnaires, counterbalance order, overall stimulation accuracy, and Sternberg working memory (WM) performance to assess target engagement).

Aim 2: Determine the effect of a 1-week course of TBS treatment (Continuous vs. Intermittent; right dlPFC target) on anxiety-related WM-deficits using the Sternberg WM paradigm during threat of shock.

Outcome measures. During each Sternberg trial, subjects will see a series of 5 or 8 letters presented singularly (encoding period) that will be followed by a brief interval where subjects are required to maintain these letters (maintenance period). At the end of the maintenance period, subjects will indicate whether the position of the letter in the series matches the number. Accuracy will be scored as the percent correct for each trial type.

Statistical Analysis. The main analysis will be a 3 [stimulation: pre-stimulation vs. post-active vs. post-sham] by 2 [protocol: cTBS vs. iTBS] repeated-measures ANOVA. As with Aim 1, we may also include several other individual difference measures as covariates in this analysis.

Aim 3: Demonstrate target engagement by measuring BOLD responses evoked by TMS pulses to the right dlPFC during threat of shock.

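### The 80% power in Section 6.2 belongs to f = 0.5 and an unnamed main effect. It is not power for a half-SD effect, nor for the iTBS-versus-cTBS contrast that Aim 1 needs.

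*Combined protocol and SAP*

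**What the plan says.** Section 6.2 gives a single power analysis for all outcomes. The effect size is "based on a moderate effect size of ($f=0.5". The other inputs are "If we set power at 0.8" and "use a corrected two-tailed alpha of 0.025", and the result is that "we would need 26 subjects per group to detect a main effect". The section does not say which main effect is meant, which test or formula was used, how f is defined, or what correlation between repeated tests was assumed. It gives no SD or raw difference.

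Section 6.1 sets the analysis for Aims 1 and 2: "The main analysis will be a 3 [stimulation: pre-stimulation vs. post-active vs. post-sham] by 2 [protocol: cTBS vs. iTBS] repeated-measures ANOVA". Stimulation is a within-subject factor and protocol is a between-subject factor.

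The Aim 1 hypothesis in Section 2, introduced with "Our hypothesis, consistent with our pilot data", is that iTBS lowers induced anxiety relative to sham and cTBS does not. Section 4.5 sets a target of 56 completers, or 28 per group.

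**The concern.** There are two gaps between the stated 80% and the use a reader will make of it.

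The first is the label. With f defined in the usual way, as the SD of the condition means over the SD of scores within a condition, 0.5 is a large shift. A half-SD difference is d = 0.5, which for two levels is f = 0.25.

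The second is the term. Power is claimed for a main effect, but an effect of iTBS and not of cTBS is a stimulation-by-protocol interaction. No power is given for that term.

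This is the plan's only power statement. If it is read as 80% power for a moderate effect on the Aim 1 question, a null interaction will look like evidence against a moderate iTBS effect, when the trial may have had a poor chance of seeing one.

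**Working it through.** **Inputs.** From Section 6.2: f = 0.5, power 0.80, two-sided alpha 0.025, 26 per group (52 in total). From Section 4.5: 28 per group. Assumed, because the documents do not give them: f = 0.25 (half an SD) as moderate, correlation ρ between a subject's tests from 0 to 0.7, equal variances and equal correlations across the three tests, and no period or carry-over effect. Powers come from the noncentral F and t distributions.

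**1. What f = 0.5 means on the SD scale.**
- Two levels: f = d/2, so d = 2 × 0.5 = 1.0 SD.
- Three levels with one shifted by d: the SD of the means is d√2/3, so d = 3 × 0.5/√2 = 1.06 SD.

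**2. Reproducing 26 per group.** Two different calculations do so.
- *A. Six independent cells, 2-df main effect*, λ = N f². At N = 51, λ = 12.75 and power is 0.809; N = 50 gives 0.7995. Rounding to two equal groups gives 52, or 26 per group, with power 0.819.
- *B. One group, three repeated levels, f from partial eta-squared*, λ = f²(n − 1)(3 − 1). At n = 26, λ = 0.25 × 25 × 2 = 12.5 and power is 0.804; n = 25 gives 0.784. The answer is 26 exactly.

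A plain two-group comparison at d = 1 needs 21 per group, so it does not reproduce the figure.

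**3. The same two calculations at f = 0.25.**
- A: λ = 52 × 0.0625 = 3.25, power 0.23. Reaching 80% would need N = 188.
- B: λ = 0.0625 × 25 × 2 = 3.125, power 0.22.

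**4. SD meaning of f = 0.5 under calculation B.** The raw-scale equivalent is 0.5√(2(1 − ρ)/3). Multiplying by 3/√2 gives a one-level shift of 0.866√(1 − ρ): 0.87, 0.72, 0.61 and 0.47 SD at ρ = 0, 0.3, 0.5 and 0.7.

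**5. The contrast Aim 1 needs.** Take each subject's active-minus-sham difference and compare it between protocols. A shift of 0.5 SD after active iTBS only, in units of the SD at one visit, is δ = 0.5/√(2(1 − ρ)) in units of the SD of that difference. The two-sample t test has noncentrality δ√(n/2).

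| ρ (assumed) | δ | Between protocols, 26 per group | Between protocols, 28 per group | 2-df interaction, 26 per group | Active vs sham within iTBS, n = 26 |
|---|---|---|---|---|---|
| 0.3 | 0.42 | 0.22 | 0.24 | 0.23 | 0.42 |
| 0.5 | 0.50 | 0.31 | 0.34 | 0.33 | 0.57 |
| 0.7 | 0.65 | 0.51 | 0.55 | 0.55 | 0.81 |

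At ρ = 0.5 the between-protocol contrast needs 78 per group (156 in total) for 80% power.

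**6. What the design detects with 80% power at alpha 0.025**, in SDs of the active-minus-sham difference. No correlation is needed here.

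| Comparison | 26 per group | 28 per group |
|---|---|---|
| Between protocols (two-sample t) | 0.88 | 0.84 |
| Within one protocol (paired t) | 0.64 | 0.61 |

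On the single-visit scale, 0.88 is multiplied by √(2(1 − ρ)): about 1.04, 0.88 and 0.68 SD at ρ = 0.3, 0.5 and 0.7.

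**7. The other direction.** For the stimulation main effect in the planned ANOVA with raw-scale f = 0.25, λ = 52 × 0.0625 × 3/(1 − ρ) = 9.75/(1 − ρ). Power is 0.70, 0.87, 0.96 and 0.999 at ρ = 0, 0.3, 0.5 and 0.7.

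**The case against.** The best defence is that the stated inputs do yield 26, by a within-subject route that fits the wording of subjects per group and a main effect at least as well as any other. On that route f = 0.5 can be close to half an SD when the correlation is high, so the label could be fair. This stands as a limit on the criticism: the 1 SD reading is conditional on raw-scale f. It does not rescue the text, because a reader cannot tell which f is meant and the two differ by up to a factor of about two (1.06 against 0.47 SD).

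It can also be said that Section 6.2 claims power only for a main effect, that the study is described as a pilot, that little was known about these effects, that the figure was to be updated before enrolment, and that recruitment may reach 75. All of this is true. But no updated figure appears in the document. With 28 per group the contrast gains only two to four percentage points (0.24, 0.34 and 0.55). The ceiling of 75 is well below the 156 needed at a correlation of 0.5. And the hypothesis remains an interaction for which no power is stated.

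Aim 1 could instead be approached through separate active-versus-sham tests within each protocol, where power is better (0.42, 0.57 and 0.81). A significant result in one group and not in the other would not show that the protocols differ.

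A reader might infer that 26 was obtained by treating each subject's three tests as different people. The documents do not support that: no method is named, and calculation B gives 26 without it. A reader might also infer that the trial is underpowered throughout. Step 7 shows otherwise for within-subject main effects.

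**Conclusion.** The point holds in this form: the 80% in Section 6.2 cannot be read as power for a moderate effect in the planned analysis. On the usual scale f = 0.5 is 1.0 to 1.06 SD, and both calculations that reproduce 26 fall to 0.22 to 0.23 at f = 0.25. For the Aim 1 contrast, a half-SD effect of iTBS alone would be missed about half to four-fifths of the time at correlations of 0.7 down to 0.3.

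The reading of moderate as half an SD is a convention, and the correlations are assumptions. The minimum detectable differences in step 6 depend on neither. Power for a moderate effect may be high or low depending on the term and the correlation, so the defect is an incomplete and mislabelled power statement that omits the hypothesised term. It is not proof that every test in the plan lacks power.

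**What to change.** Rewrite the paragraph in Section 6.2 and leave enrolment as it is.

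1. Drop the word moderate. State the test, the term tested, the definition of f and the assumed within-subject correlation.
2. Add what the design detects with 80% power at alpha 0.025 for the stimulation-by-protocol contrast: 0.88 SD (26 per group) or 0.84 SD (28 per group) of the active-minus-sham difference between protocols, and 0.64 or 0.61 SD within one protocol.
3. Convert these to startle and accuracy units where the pilot data mentioned in Section 2 provide an SD and a correlation. Where they do not, show a range.
4. Do not write that 26 came from a between-subjects calculation. Only the authors of the plan can say how it was obtained.

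The cost is one paragraph and no subjects. The downside is that the stated power becomes less favourable.

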7.1 Definitions

7.1.1 Adverse Event

*An **adverse event** (AE) is any symptom, sign, illness or experience that develops or worsens in severity during the course of the study. Intercurrent illnesses or injuries should be regarded as adverse events. Abnormal results of diagnostic procedures are considered to be adverse events if the abnormality:*

- *results in study withdrawal*
- *is associated with a serious adverse event*
- *is associated with clinical signs or symptoms*
- *leads to additional treatment or to further diagnostic tests*
- *is considered by the investigator to be of clinical significance*

7.1.2 Serious Adverse Event

Serious Adverse Event

*Adverse events are classified as serious or non-serious. A **serious adverse event** is any AE that is:*

- *fatal*
- *life-threatening*
- *requires or prolongs hospital stay*
- *results in persistent or significant disability or incapacity*
- *a congenital anomaly or birth defect*
- *an important medical event*

Important medical events are those that may not be immediately life threatening, but are clearly of major clinical significance. They may jeopardize the subject, and may require intervention to prevent one of the other serious outcomes noted above. For example, drug overdose or abuse, a seizure that did not result in in-patient hospitalization, or intensive treatment of bronchospasm in an emergency department would typically be considered serious.

CONFIDENTIAL

All adverse events that do not meet any of the criteria for serious should be regarded as non-serious adverse events.

7.2 Recording of Adverse Events

All adverse events will be recorded by the study team via the adverse event source document, and summarized in the enrollment log. All adverse events will be reported by the study staff to the PI within 4 days.

7.3 Relationship of AE to Study

Relatedness to the research of all serious adverse events will be determined by the medical advisor.

7.4 Reporting of Adverse Events, Adverse Device Effects and Unanticipated Problems

7.4.1 Follow-up report

If an SAE has not resolved at the time of the initial report and new information arises that changes the investigator's assessment of the event, a follow-up report including all relevant new or reassessed information (e.g., concomitant medication, medical history) will be submitted to the IRB. The PI is responsible for ensuring that all SAE are followed until either resolved or stable.

7.4.2 Investigator Reporting

The medical advisor will determine whether the event represents a severe adverse event (SAE) or an unanticipated problem (UP). SAEs and UPs will be reported to the IRB and DSMB within 7 days. Mild and Moderate adverse events will be logged and reported to the IRB annually and the DSMB quarterly.

7.5 Stopping Rules

The study will be suspended if there is any UP or SAE until IRB reviews the event and approves continuation.

7.5.1 Data and Safety Monitoring Plan

The Principal Investigator is responsible for detecting, documenting, and reporting unanticipated problems (UPs), adverse events (AEs), including serious adverse events (SAEs), and deviations in accordance with NIH policy, IRB requirements, and federal regulations. Relatedness to the research of all serious adverse events will be determined by the medical advisor.

CONFIDENTIAL

In addition, the PI will maintain a full FDA regulatory binder tracking subject enrollment, qualifications of investigators, IRB correspondence, inclusion/exclusion criteria, and all source data. All essential data will be recorded in the electronic case report form by the study staff. Acknowledgement of incomplete data records will be noted in the screening and enrollment log. Pilot subjects, subjects who withdraw, or subjects who experience an adverse event are expected to have incomplete data records, and will be excluded from the final analysis.

Site monitoring is conducted to ensure that the rights and well-being of trial participants are protected, that the reported trial data are accurate, complete, and verifiable, and that the conduct of the trial is in compliance with the currently approved protocol/amendment(s), with International Conference on Harmonisation Good Clinical Practice (ICH GCP), and with applicable regulatory requirement(s).

- Monitoring for this study will be performed by an in-house individual trained by the office of clinical research.
- The first subject will be monitored. Then 30% of all subsequent subjects will be monitored.
- Monitored subjects will be selected randomly during the yearly monitoring visit conducted prior to continuing review.
- The following data will be reviewed for all monitored subjects:
 - Informed consent and documentation of consent
 - Verification of eligibility
 - SAE (Serious Adverse Events) reported to IRB
 - Primary and secondary outcome measures
- Details of clinical site monitoring are documented in a Monitoring Plan (MP). The MP describes in detail who will conduct the monitoring, at what frequency monitoring will be done, at what level of detail monitoring will be performed, and the distribution of monitoring reports.
- Independent audits or compliance reviews may be conducted by the Office of clinical Research to ensure that monitors are following the MP.

8 Study Administration, Data Handling and Record Keeping

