4.5 Total Number of Subjects and Sites

The target number of completers will be N=56. We anticipate that about 20% of subjects (N=11) will terminate the study during the task because of discomfort and another 10% (N = 5) to withdraw due to scheduling issues. An additional 3 subjects per experiment (n=3) will be included for piloting.

4.6 Vulnerable Populations:

All subjects must be able to provide their own consent. This study is above minimal risk and we do not want to enroll participants who do not understand the risk/benefit ratio of the study, particularly when there is no benefit to the participants. For this reason we exclude people with IQ lower than 80. We exclude and rule out pregnant women because of the unknown effects of the shocks and of the fMRI on the developing fetus. We exclude non-English speakers since not all the instruments and test we use are translated and validated in Spanish or other languages. Based on our experience, we made the decision that 50 would be the upper age limit to prevent age-related changes in brain structure and function from confounding our analyses. Patients will not be taken off medications for the purpose of the study.

CONFIDENTIAL

5 Study Procedures

Does your study use MRI? (CAMRIS is the appropriate contact for all studies involving MRIs)

Yes No

Check of all that apply:

1.5T MRI
 3T MRI
 7TMRI

Does the MRI use investigational sequences and/or coils?
(See Experimental Device Clause)

Yes No Unsure (if unsure you need to contact CAMRIS)

Experimental Device Clause -- Some of the pulse sequences and/or RF coils are not FDA approved but are considered to pose no more than minimal risk.

Does your study include pregnant women?
(See Pregnancy Clause and Justification)

Yes No

Pregnancy Clause -- Although there are no known risks related to MRI on pregnant women or a fetus, there is a possibility of yet undiscovered pregnancy related risks. Since there is no possible benefit from participating in this protocol for a pregnant woman, we will exclude pregnant women.

Does the MRI require the use of Contrast Agents?
(See Contrast Risks)

Yes No

Does your study involve the exposure to radiation, radiotracers and/or radiological imaging modalities?

Yes No (If No, no RRSC review is needed)

Will any of the radiation exposure result from procedures that are or could be performed solely as a result of a subject's participation in the research protocol?

Yes No

CONFIDENTIAL

Ultrasound

Yes

No

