- The most common side effect of TMS is a mild headache, jaw pain, or other facial discomfort, which approximately 25% of patients experience. We will demonstrate TMS at the initial screening visit to make sure the subject is comfortable receiving this procedure. The TMS that will be used in this research is not expected to carry any more than the limited potential for these risks listed above.

Rare:

- Subjects may experience temporary and local bruising, swelling or pain from the swim cap and/ or muscle activation by TMS.
- Although uncommon, some subjects have experienced nausea during the experiment.
- In patients with epilepsy, TMS could result in a seizure. Patients with stroke may also be at increased risk for a seizure due to brain scarring. Therefore, those with history of epilepsy or stroke will be excluded from TMS studies. For a typical healthy person, producing a seizure from TMS in this experiment is very unlikely.
- The TMS device produces a clicking sound. Although studies have found no hearing impairments as a result of this sound, some subjects' experience a mild temporary effect on their hearing. To minimize this possibility, you will be given protective earplugs.
- Objects such as watches and credit cards should be removed as these could be damaged.
- The effects of TMS on a fetus are unknown. Therefore, we require that females of child-bearing potential attest at the time of participation that they are not pregnant.

Alternatives to participation: The studies proposed in this project do not involve an intervention, so the participants will not directly benefit from the research. Therefore, there are no alternatives to participation. However, participants will be free to withdraw from the

CONFIDENTIAL

study without consequence.

Protections against risk

Electric Shock: Shock will be delivered at a level that is judged by the subject as unpleasant but not painful. Study shock levels will be determined before the test begins. The subject may stop the experiment at any time if they find the discomfort to be too great.

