TMS: To minimize the likelihood of seizures we will 1) conform to the guidelines set in the workshop convened by the National Institute for Neurological Disorders and Stroke (NINDS) in 1996 (Rossi et al., 2009), and 2) screen subjects for risk factors using the TMS adult safety screen questionnaire (Keel et al., 2000). In addition, we will train all personnel to recognize potential seizures, and administer appropriate care. In the event that the TMS operator observes symptoms of a seizure he or she will 1) stop the protocol and inquire about the subject's well-being, 2) apply first-aid if the subject is unresponsive, 3) ensure the subject is physically safe for the duration of the seizure, 4) call 911. If the subject develops a headache during or immediately after the stimulation, this will be managed with over-the-counter pain medication. To minimize the likelihood of hearing loss or tinnitus, subjects will wear hearing protection for the duration of the rTMS session. Risks to the unborn children of pregnant women receiving MRI and TMS are unknown. Pregnant women will be excluded as per IRB policy.

MRI: The potential risks related to MRI will be minimized as follows: 1) Claustrophobia associated with MRI will be reduced by explaining the nature of the procedure in detail prior to subject enrollment; and 2) a possible history of any intraocular, intra-aural, intracranial, or intrathoracic metal will exclude the subject from the study. Earplugs will be given to each subject to wear during the scan to minimize discomfort and prevent any adverse effects on hearing resulting from the scanning procedure.

A radiology technologist (or trained individual authorized to run the scanner) and a clinician will be present throughout the MRI study in case medical emergencies would arise. During MRI scanning, the subject can communicate with the control room personnel via an intercom at the operating console. Thus, the subject can be removed immediately from the MRI scanner, if necessary.

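### Section 7.5.1 as written removes from the final analysis every subject who withdraws or has any adverse event, including completers with full data

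*Combined protocol and SAP*

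**What the plan says.** The only rule on who enters the final analysis is in the monitoring text of section 7.5.1. After pilot subjects, it lists two further groups: "subjects who withdraw, or subjects who experience an adverse event are expected to have incomplete data records, and will be excluded from the final analysis".

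Other sections determine how far that rule reaches:

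- Section 7.1.1: an adverse event "is any symptom, sign, illness or experience that develops or worsens in severity during the course of the study". There is no threshold for severity or relatedness.
- Section 7.2 has all adverse events recorded, and section 7.4.2 adds: "Mild and Moderate adverse events will be logged and reported to the IRB annually and the DSMB quarterly".
- Section 10.1, on TMS risks: "The most common side effect of TMS is a mild headache, jaw pain, or other facial discomfort, which approximately 25% of patients experience".
- Section 10.1, on protections: "If the subject develops a headache during or immediately after the stimulation, this will be managed with over-the-counter pain medication". Withdrawal is not mentioned.
- Section 4.5 targets 56 completers and expects that "about 20% of subjects (N=11) will terminate the study during the task because of discomfort", with 5 more lost to scheduling and 3 pilots.
- Section 6.2: "we would need 26 subjects per group to detect a main effect".

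Section 6.1 names a 3 × 2 repeated-measures ANOVA (stimulation by protocol) for Aims 1 and 2. It gives neither an analysis population nor a method for missing data.

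**The concern.** The sentence presumes that subjects with an adverse event have incomplete records, then excludes them whether or not they do. That presumption does not fit the protocol's account of its commonest TMS side effect, which is mild and managed with over-the-counter medication. An analyst following the text would discard complete, usable data because of an event that can follow stimulation and randomisation.

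Each subject receives both active and sham courses, so exclusion removes both and the within-person contrast stays paired. Three harms remain:

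- The active-versus-sham effect is estimated only in people who tolerated everything without a symptom.
- Protocol (cTBS or iTBS) is randomised between subjects, and the section 2 hypothesis compares the protocols: "we expect excitatory but not inhibitory TBS (compared to sham) to reduce induced anxiety". If adverse event or withdrawal rates differ by protocol or by treatment order, exclusion undoes the balance that allocation created.
- Usable visits are lost. The sample-size text budgets for withdrawals but names no allowance for completers removed because of an adverse event.

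Not every such event reflects stimulation. Some may come from the shocks, the startle noise or the MRI, and some may occur at Lab Visit 1, before any TBS.

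**Working it through.** **1. Does the rule reach completers?** Any new symptom is an adverse event (7.1.1), all are recorded (7.2), and mild ones are logged (7.4.2). A headache after stimulation is treated, with no mention of withdrawal (10.1). A subject can therefore have a logged adverse event and full data at all three test visits. Section 7.5.1 excludes that subject, and nothing in section 6 says otherwise.

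**2. The plan's own figures.**

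- Recruitment (4.5): 56 + 11 + 5 + 3 = 75, which matches. Non-pilot subjects: 75 − 3 = 72. Discomfort accounts for 11 of the 16 planned withdrawals (69%).
- Recruitment (6.2): 2 × 26 = 52; 52 × 1.15 = 59.8, rounded up to 60; 60 + 3 = 63, which matches.
- Required n (6.2): 26 per group does not reproduce. For two groups, f = 0.5 means d = 2f = 1.0. At two-sided alpha 0.025 and power 0.80, the non-central t gives 21 per group, and power at 26 is 0.898. This is a separate matter, but it affects how the power figures below read.

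**3. Completers left.** The adverse event rate r among completers is an assumption; the 25% in section 10.1 is a general TMS figure. Remaining = 56 × (1 − r).

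| Assumed r | Remaining of 56 | Share of 72 non-pilot subjects |
|---|---|---|
| 5% | 53.2 | 74% |
| 10% | 50.4 | 70% |
| 25% | 42.0 | 58% |
| 40% | 33.6 | 47% |

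The 25% row assumes that adverse events among completers are unrelated to the discomfort dropouts. At the other extreme, 72 × 0.25 = 18 subjects have an event and all 11 discomfort dropouts are among them. Then 18 − 11 = 7 completers are removed and 56 − 7 = 49 remain, still below 52.

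**4. Rate at which the set falls below 52.** (56 − 52)/56 = 7.1%. If sessions are independent (an assumption), the chance per TBS session that reaches this over 8 sessions is 1 − (52/56)^(1/8) = 0.92%. Over all 12 visits it is 1 − (52/56)^(1/12) = 0.62% per visit. If events cluster within people, a higher per-session chance would be needed.

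**5. Power.** Two-group t-test, two-sided alpha 0.025, as a stand-in for the planned ANOVA. The second effect size, d = 0.878, is the one for which 26 per group gives 0.80.

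| n per group | Total | Power, d = 1.0 | Power, d = 0.878 |
|---|---|---|---|
| 28 | 56 | 0.92 | 0.83 |
| 26 | 52 | 0.90 | 0.80 |
| 21 | 42 | 0.82 | 0.70 |
| 17 | 34 | 0.71 | 0.59 |

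**6. Can the proposed model be fitted?** Its fixed effects are intercept (1), protocol (1), stimulation (2), interaction (2) and second versus first post-stimulation visit (1), 7 columns with rank 7. A three-level visit factor would not work: baseline is both a stimulation level and a visit level, so intercept, stimulation and visit give 5 columns of rank 4.

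**The case against.** The best counter-argument is context. The sentence sits in a monitoring section, directly after one about noting incomplete records in the log, so the authors may have meant to exclude only subjects whose records are in fact incomplete. That intent is possible. The sentence does not state it as a condition, however, and no other section supplies one. Even on the narrower reading, usable visits from withdrawn subjects are thrown away.

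A second argument is that excluding withdrawals is an openly planned completer analysis in a mechanistic pilot. Withdrawals are budgeted, the three-level ANOVA needs all three test visits, and a subject with only baseline data says little about active versus sham. This is fair as far as numbers go. It does not answer the selection problem: 11 of the 16 expected withdrawals are for discomfort, which is unlikely to be unrelated to response in an anxiety experiment.

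Third, the harm is partly limited and partly unmeasured. The active–sham pairing survives, power holds at moderate rates under the stated effect size, and no section says that tolerability differs by protocol. All of this stands. So does the point that 52 is a soft benchmark, since the stated inputs need only 42. The 15% unusable-data allowance in 6.2 might absorb some loss, but it is not described as covering adverse events.

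Finally, a one-clause edit tying exclusion to missing data would cure the adverse event part without changing the model. It would still leave partial data from withdrawals unused.

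**Conclusion.** The concern holds. Taken literally, section 7.5.1 selects the analysis set on adverse events and withdrawal, both of which can occur after randomisation and stimulation, and nothing elsewhere limits it. It governs every primary analysis and should be corrected before outcomes are seen; otherwise whether a logged mild symptom removes a subject could be decided with the data in view.

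The set falls below the protocol's 52 once more than 4 of 56 completers (7.1%) have an adverse event. Power is the lesser issue: at f = 0.5 it drops below 0.80 only at rates above 25%, though an effect of d = 0.878 would leave 0.70 at 21 per group. These figures rest on an assumed adverse event rate among completers, equal group sizes and a two-group test in place of the 3 × 2 ANOVA. The documents do not allow the size or direction of any bias to be calculated.

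**What to change.** - **Section 7.5.1:** delete the exclusions for adverse events and withdrawal; keep only the pilot exclusion.
- **Section 6.1, analysis set:** state that all randomised non-pilot subjects with usable test-visit data are analysed as randomised, regardless of adverse events.
- **Section 6.1, model:** replace the listwise ANOVA with a linear mixed model. Fixed effects are protocol, stimulation (pre, post-active, post-sham), their interaction, and one term for the second versus the first post-stimulation visit; subject is a random effect. The interaction tests whether the effect of stimulation differs between iTBS and cTBS.
- **Reporting:** give the completer analysis as a sensitivity analysis, and tabulate adverse events by protocol and by active or sham period.

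The cost is wording in two sections and a different model; no extra data are collected. The drawback is that withdrawals are then handled under a missing-at-random assumption, which should be stated, and subjects with only a baseline visit contribute little to the active–sham contrast.
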